11.3 Essential Records Retention

The Investigator should maintain the essential clinical study documents (including CRFs, source documents, clinical drug disposition records, signed subject informed consent forms, AE reports and other regulatory documents) as required by the applicable national regulatory requirements. The Investigator is to take adequate measures to prevent accidental or premature destruction of these documents. In the event of accidental destruction, the Investigator should notify the Sponsor (or an authorized representative) immediately.

Essential clinical study documents will be retained at least two (2) years after the last approval of a marketing application in an ICH region and until there are no pending or contemplated marketing applications in an ICH region OR at least two (2) years have elapsed since the formal discontinuation of clinical development of the investigational product. These documents shall be retained for a longer period, however, if required by the applicable regulatory requirements or by an agreement with the Sponsor (or an authorized representative).

The Investigator is required to notify the Sponsor (or an authorized representative) prior to changing the location or status of any essential clinical study documents. The Sponsor (or an

authorized representative) will be responsible for informing the Investigator as to when these documents no longer need to be retained.

11.4 Investigator Agreement

The Investigator is responsible for assuring the proper implementation and conduct of the clinical study including those study-related duties delegated to other appropriately qualified individuals. The Investigator and his/her staff will cooperate with the Sponsor (or an authorized representative) during monitoring and auditing visits to assist with the review of the study data and resolve any discrepancies.

The Investigator will demonstrate due diligence in recruitment and screening of potential study subjects. The enrollment rate should be sufficient to complete the study as agreed with the Sponsor (or an authorized representative). The Sponsor (or an authorized representative) is to be notified of any projected delays, which may impact the completion of the study.

The Sponsor retains the right to terminate the clinical study at any time for any reason. In such an event, instructions on the requirements for the discontinuation of subjects will be provided by the Sponsor (or an authorized representative).

12 SPONSOR OBLIGATIONS

12.1 Protocol Amendments

Only the Sponsor (or an authorized representative) will make modifications to the clinical study protocol, which will be documented in a written amendment that describes all changes that will be implemented. Protocol amendments will be categorized as either substantial or non-substantial.

Protocol amendments will be considered substantial when the changes have significant impact on:

- The safety of physical or mental integrity of the subjects
- The scientific value of the study
- The conduct or management of the study
- The quality or safety of any investigational medicinal product or control used in the study

Protocol amendments will be considered non-substantial when the changes affect only administrative issues with the conduct of the study, i.e. changes in telephone numbers or addresses.

The Sponsor (or an authorized representative) will be responsible for notifying the appropriate national regulatory authorities in writing of any amendments to the protocol prior to the changes being implemented except in those cases where the changes are necessary to eliminate an immediate hazard to the clinical study subjects.

Substantial amendments will require written approval by the IEC/IRB prior to being implemented by the Investigator at the study site except under those circumstances described previously. Non-substantial amendments will not require approval by the IEC/IRB unless requested by the IEC/IRB.

12.2 Study Monitoring

The study will be monitored by authorized representatives of the Sponsor throughout its duration by means of personal visits to the Investigator's facilities and through other communications (e.g. telephone calls, written correspondence). Monitoring visits will be scheduled at mutually agreeable times periodically throughout the study and at frequency deemed appropriate for the study.

These visits will be conducted to evaluate the progress of the study, ensure the rights and well-being of the subjects are protected, check that the reported clinical study data are accurate, complete and verifiable from source documents, and the conduct of the study is in compliance with the approved protocol and amendments, GCPs and applicable national regulatory requirements. A monitoring visit will include a review of the essential clinical study documents (regulatory documents, CRFs, source documents, drug disposition records, subject informed

consent forms, etc.) as well as discussion on the conduct of the study with the Investigator and staff. The Investigator and staff should be available during these visits to facilitate the review of the clinical study records and resolve/document any discrepancies found during the visit.

12.3 Quality Assurance Audits

The Sponsor's (or an authorized representative's) Quality Assurance department may conduct on-site audits of all aspects of the clinical study either during the study or after the study has been completed.

The clinical study may also be subject to inspection by regulatory authorities (national or foreign) as well as the IECs/IRBs to ascertain that the study is being or has been conducted in accordance with protocol requirements, GCPs, as well as the applicable regulatory requirements.

13 PUBLICATION POLICY

The data generated by this study are confidential information of the Sponsor. The Sponsor will publicly disclose the results of all applicable clinical trials following legal and regulatory requirements. The publication policy with respect to the Investigator and study center will be set forth in the Clinical Trial Agreement.

14 INSURANCE

The Sponsor has taken out a liability insurance, which covers this study as required by local law and/or national regulations and/or ICH guidelines whichever is applicable.

1. ABBREVIATIONS

1.1 Standard Abbreviations

AE	adverse event
ANCOVA	analysis of covariance
ATC	Anatomical Therapeutic Chemical (class)
AUC	area under the curve
BDR	blind data review
bpm	beats per minute
ĊRF	case report form
CRO	contract research organization
CV	coefficient of variation
DBP	diastolic blood pressure
DDT	data definition table
DSMB	data safety monitoring board
ECG	electrocardiogram
FA	Full Analysis
FDA	food and drug administration
Geo. mean	geometric mean
GOP	global standard operating procedure
HLGT	High Level Group Term
HLT	High Level Term
ICH	International Conference on Harmonization
LDA	day number of the last day of drug administration
LLOQ	lower level of quantification
LLT	Lowest Level Term
LOCF	last observation carried forward
max	maximum
MedDRA	Medical Dictionary for Regulatory Activities
min	minimum
N,n	number of observations
NA	not applicable
OC	observed cases
PD	pharmacodynamic
РК	pharmacokinetic
PP	Per Protocol
PT	Preferred Term
QOL	quality of life
SAE	serious adverse event
SAP	statistical analysis plan
SBP	systolic blood pressure
SD	standard deviation
S.I.	System International
SOC	System Organ Class

SOP	standard operating procedure
TARC	Therapeutic Area Review Committee
TEAE	treatment-emergent adverse event
TESAE	treatment-emergent serious adverse event
TLF/T,L,F	tables, listings and figures
ULOQ	upper limit of quantification
URL	upper reference limit
WC	windowing convention
WHO-DD(E)	World Health Organization – Drug Dictionary (enhanced)

6

2. Introduction

3. SUMMARY OF THE PROTOCOL

3.1 Overall Study Plan

This is a controlled, open-label, parallel-group study evaluating the efficacy and safety of Racecadotril in infants, children and adolescents with acute diarrhea. The number of subjects to be screened is 150 in order to enroll 124 subjects for either standard treatment (oral rehydration solution, ORS) alone or ORS plus Racecadotril.

1.5 mg/kg of Racecadotril will be administered, 3 times daily, via the oral route. Study drug intake will start either with the noon or the evening dose on day 1.

In infants less than 9 kg: one 10 mg sachet 3 times daily. In infants from 9 kg to <13 kg: two 10 mg sachets 3 times daily. In children from 13 kg to 27 kg: one 30 mg sachet 3 times daily. In children from more than 27 kg to 60 kg: two 30 mg sachets 3 times daily. In children or adolescents of 60 kg or higher: 100 mg capsule 3 times daily

Standard treatment is oral rehydration solution (ORS) according to the registered local label and the instruction of the investigator. The same brand of ORS and the same age-appropriate standardized treatment pattern for the subjects will be applied throughout the trial. ORS treatment and dosing will be documented in the CRF.

Screening and Enrolment (Day 1, Visit 1)

Subjects presenting with acute diarrhea will be evaluated for eligibility. They will undergo a physical examination including assessment of dehydration level, vital signs, a review of their medical history and concomitant medication. If the subjects are eligible for the study, demographics, number of stools during the last 24 hours will be assessed as baseline values. The subjects will be randomized to Racecadotril plus ORS or ORS alone. On Day 1 the subject will start with study treatment. The starting dose will either be the noon or the evening dose depending on the timing of Visit 1.

Treatment period (until recovery, maximally 5 days)

Subjects will be treated with Racecadotril tid according to the body weight dose requirement on an in- or out-patient basis for maximum 5 days. One arm will be treated with ORS alone as standard treatment, the other treatment arm will be treated with ORS (according to the registered local label and the instruction of the investigator) in addition to Racecadotril. ORS will be prescribed by the investigator and will be taken according to the product label and the instruction of the investigator(s) will be instructed to stop study drug treatment when the patient recovered. On each day, the parent(s)/caregiver(s) will fill in their diaries, documenting the date and time of each individual stool, the stool consistency of each stool (diarrheal/watery or normal), the amount of ORS and the study drug intake. After the occurrence of two consecutive normal stools, the parent(s)/caregiver(s) can stop recording of the diary and return to the study site for the end of treatment visit. The date of recovery is the day when the first of two consecutive normal stools were excreted. AEs are to be reported on an ongoing basis.

End of treatment (Day 6 or early recovery, Visit 2)

The last dose of study drug will be the morning dose of day 6, if not recovered earlier. The same day, or within 24 hours after recovery, the parent(s)/caregiver(s) will visit the site for the end of treatment visit of the child. Data on vital signs, AEs, physical examination and concomitant medication will be collected. Subjects will return their diaries and unused medication.

Safety follow-up

A phone call will be performed at 5-7 days after end of the treatment period for the safety follow-up.

3.2 Study Flowchart

The flowchart of the study can be found in Appendix 9.1.

3.3 Study Objectives

Primary Objective(s)

The primary objective is to evaluate the efficacy of Racecadotril in addition to standard treatment oral rehydration solution (ORS) versus ORS alone in infants, children and adolescents (3 months until <18 years) with acute diarrhea measured as duration of diarrhea (hours) between the start of treatment until final diarrheal/watery stool before recovery or end of study treatment (treatment duration maximal 5 days).

Duration of diarrhea is defined by date and time of the evacuation of the final watery/diarrheal stool before recovery derived from the daily diary (see Figure 3-2 Duration of diarrhea and Time until recovery definition).

First dose of study

Figure 3-2 Duration of diarrhea and Time until recovery definition

Secondary Objective(s)

- Number of recovered subjects per treatment group in total and until each individual treatment day. Mean and median time until recovery per treatment group.
- Time until recovery, defined by date and time of the evacuation of the first of two consecutive normal stools or no stool within 12 hours after first normal stool (see Figure 3-2 Duration of diarrhea and Time until recovery definition).
- Global Physician Assessment at the end of treatment:
 - \circ 1 = Complete relief of acute diarrhea,
 - \circ 2 = marked improvement of acute diarrhea,

- \circ 3 = moderate improvement of acute diarrhea,
- 4 =slight improvement of acute diarrhea,
- \circ 5 = no change in acute diarrhea,
- \circ 6 =worsening of acute diarrhea. (Treatment success = GPA score of 1 or 2).
- For toilet trained children and adolescents: number of stools per day as well as number of watery stools per day from start of treatment and until end of study treatment.

Safety Objective(s)

To evaluate the safety and tolerability of Racecadotril together with oral rehydration solution (ORS) versus ORS alone in infants, children and adolescents with acute diarrhea by adverse events, physical examination and vital signs.

4. STATISTICAL ANALYSIS

4.1 Subject samples

There will be five subject samples.

- The all subjects consented sample will consist of all subjects who:
 - Gave their informed consent.
- The all subjects allocated to treatment sample will consist of all subjects who:
 - Were in the all subjects consented sample; and
 - Were allocated to treatment.
- The safety sample will consist of all subjects who:
 - Were in the all subjects allocated to treatment sample; and
 - Had at least one dose of study medication administered.
- The full analysis (FA) sample will consist of all subjects who:
 - Were included in the safety sample; and
 - Had data for at least one post-baseline assessment of any efficacy measurement.
- The per-protocol (PP) sample will be defined through blind data review and will consist of all subjects who:
 - Were included in the FA sample; and
 - Did not present any major protocol violation (consideration about exclusion of patients from *the PP sample* will be performed at the Blind Data Review).

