4.2 Efficacy analysis

The *FA subject sample* will be used for the analysis of the efficacy data. Additionally, primary efficacy results analysis will be conducted on the *PP sample* as the sensitivity analysis. Descriptive statistics will be presented by treatment arm and by stratification level (Age Category) for all planned efficacy endpoints.

All analyses will be based on available data only and no missing data will be imputed.

All parameters will be summarized using descriptive statistics and listed.

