4.2.1 Primary Efficacy Analysis

The primary efficacy variable is the duration (hours) of diarrhea (treatment duration max 5 days). Duration of diarrhea is defined by date ("event" date) of the evacuation of the last diarrheal/watery stool before recovery.

In order to compare the primary efficacy parameter, duration of diarrhea, between the treatment groups, a Kaplan Meier (KM) analysis will be performed. The KM algorithm will be applied to derive the median duration and the 95% confidence intervals for the median, Q1, Q3 and mean duration with Greenwood's estimator of standard deviation of Kaplan-Meier estimator.

The log-rank test will be used to test whether the difference between the duration of diarrhea between two treatment groups is statistically significant, i.e. p-value <0.05.

For duration estimation the date and time of first drug intake will be assumed as start time point and all subjects without "event" will be censored by 6 days (144 hours).

SAS code for the analysis:

PROC LIFETEST DATA = [dataset name] METHOD=KM PLOTS=SURVIVAL OUTSURV=SURV CONFTYPE=LOGLOG ATRISK; TIME [time variable]*[censor variable]; STRATA [arm variable];

RUN;

The "OUTSURV=SURV" statement provides variables that contains the lower and upper limits of the pointwise confidence intervals for the survivor function ("SDF_LCL" and "SDF_UCL"), this confidence intervals should be transformed for tables as follows:

[Lower limit var name] = round(100*(1-SDF_UCL),.1); [Upper limit var name] = round(100*(1-SDF_LCL),.1);

As a first sensitivity analysis, duration of diarrhea will be analyzed by age subgroups as follows:

- Racecadotril + ORS (age subgroup 3 to < 24 month) vs ORS (age subgroup 3 to < 24 month) comparison;
- Racecadotril + ORS (age subgroup >= 2 to <12 years) vs ORS (age subgroup >= 2 to <12 years) comparison;
- Racecadotril + ORS (age subgroup 12 to < 18 years) vs ORS (age subgroup 12 to < 18 years) comparison;

As a second sensitivity analysis, duration of diarrhea will be analyzed by weight/dosing subgroups as follows:

• Racecadotril + ORS (Infants less than 9 kg) vs ORS (Infants less than 9 kg) comparison;

- Racecadotril + ORS (Infants from 9 kg to < 13 kg) vs ORS (Infants from 9 kg to < 13 kg Infants from 9 kg to < 13 kg) comparison;
- Racecadotril + ORS (Children from 13 kg to 27 kg) vs ORS (Children from 13 kg to 27 kg) comparison;
- Racecadotril + ORS (Children from more than 27 kg to 60 kg) vs ORS (Children from more than 27 kg to 60 kg) comparison;

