5.3 Efficacy data

The efficacy data collected are:

- Information about diarrheal/watery stool/stool from Subjects Diary (domain SS);
- Global physician assessment at the end of treatment (domain QS).

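### Read literally, the SAP censors a child who has a physician rating but no usable diary at 144 h, as if diarrhea had been observed throughout

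*SAP*

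**What the plan says.** - **Entry to the FA sample (SAP 4.1).** The child must be in the safety sample ("Had at least one dose of study medication administered") and "Had data for at least one post-baseline assessment of any efficacy measurement".
- **What counts as efficacy data (SAP 5.3).** There are two sources: the stool diary and, in its own domain, "Global physician assessment at the end of treatment (domain QS").
- **Which sample is used (SAP 4.2).** The FA sample "will be used for the analysis of the efficacy data". No further diary requirement is set for the primary endpoint.
- **Where the event comes from (SAP 3.3).** Duration runs to the "final watery/diarrheal stool before recovery derived from the daily diary".
- **Censoring (SAP 4.2.1).** The start is the first drug intake, and "all subjects without 'event' will be censored by 6 days (144 hours").
- **Missing data (SAP 4.2).** "All analyses will be based on available data only and no missing data will be imputed".

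Time until recovery uses the same Kaplan-Meier method (SAP 4.2.2). The Cox model covers both durations (SAP 4.2.3).

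**The concern.** The censoring sentence does not separate a child who was observed and had not recovered from a child whose stools were not observed at all. A child who attends the end-of-treatment visit and is rated by the physician, but whose diary is lost or unusable, qualifies for the FA sample on the rating alone and then has no event. That child can be a success in the Fisher test of the GPA and a non-recovery in the log-rank test, the Kaplan-Meier curves, the time-to-recovery analysis and the Cox model.

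If such losses are balanced, both curves are pulled down and some power goes. If they fall mainly in one arm, the comparison itself is biased: against ORS when control diaries are missing, and against racecadotril when its diaries are missing. The trial is open-label (Protocol 7.6), so the handling should be fixed before anyone sees which children are affected.

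**Working it through.** **1. The rules side by side.** A GPA is an efficacy measurement, so one dose plus a GPA gives FA membership. No diary means no dated stool, hence no event. No event means 144 h, censored. The only competing text is the available-data sentence in SAP 4.2, which does not say that such a child leaves the primary analysis.

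**2. What 144 h does.** Treatment runs from the noon or evening dose of Day 1 to the morning dose of Day 6. With assumed clock times of 12:00 and 08:00, the longest window is 5 × 24 − 4 = 116 h. Even to midnight at the end of Day 6 it is 5 × 24 + 12 = 132 h. A time of 144 h lies beyond both, so the child stays in the risk set at every event time in the window.

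**3. The plan's own figure.** Protocol 10.8 gives 55 per group, 62 after drop-out. The Freedman formula reproduces this when the 72 h recovery percentages are entered as event-free proportions:
- ratio = ln 0.842 / ln 0.594 = 0.330
- events = (1.960 + 0.842)² × (1.330/0.670)² ≈ 31.0 (ratio unrounded)
- mean event probability = (0.406 + 0.158)/2 = 0.282
- n = 31.0/(2 × 0.282) ≈ 54.9, so 55; then 55/0.9 = 61.1, so 62.

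**4. Simulation inputs.** There are 62 per arm. Event times are drawn from the recovery table in Protocol 10.8 (24, 50, 72, 96 and 120 h), interpolated linearly, with non-recovered children censored at 144 h. The test is the two-sided log-rank test at 0.05. Under the null, both arms follow the placebo column. In each arm, m recovered children are chosen at random and either censored at 144 h (literal rule) or left out. The documents give no diary-loss rate, so m = 0 to 6 (about 0 to 10% of 62) is an assumption. Runs used 1,500 to 8,000 trials per scenario. At 1,500 trials the standard error is √(0.5 × 0.5/1500) = 1.3 points at 50% and √(0.2 × 0.8/1500) = 1.0 point at 20%.

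**5. Results.**

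| Truth | Diaries lost (ORS, racecadotril) | Censored at 144 h | Left out |
|---|---|---|---|
| Planned effect, power | 0, 0 | 96-97% | same |
| | 3, 3 | 93-94% | 97% |
| | 6, 6 | 90-91% | 95% |
| | 0, 3 | 82-83% | 95% |
| | 0, 6 | 50-51% | 94-95% |
| No effect, one-sided false positives for racecadotril | 0, 0 | 2.5% | same |
| | 3, 0 | 8% | 3.2% |
| | 6, 0 | 20-21% | 4.5% |
| | 3, 2 | 3.5% | not run |
| | 6, 4 | 4.1% | not run |
| | 3, 3 | 1.9% | not run |

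The two-sided error under no effect is 8.7% (3, 0) and 20% (6, 0) if censored, against 5.5% and 5.3% if left out.

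**6. The curves.** With three lost per arm, medians move from 63.4 to 66.3 h (ORS) and from 28.4 to 31.0 h (racecadotril). At 10% loss, 120 h recovery becomes 0.9 × 80.6% = 72.5% and 0.9 × 94.7% = 85.2%. The ORS curve then never reaches 75%, so the upper quartile that SAP 4.2.1 asks for cannot be estimated in that arm.

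**The case against.** **SAP 4.2 may already settle it.** Under an available-data rule, a child with no stool record has no primary value and would simply be absent. This is a fair reading, so it cannot be said as settled fact that the trial will censor these children. But the 144 h sentence is the more specific rule and covers every subject without an event. The two readings give different primary datasets.

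**The per-protocol (PP) analysis may remove them.** The primary analysis is repeated on the PP sample, and a child without a diary is an obvious candidate for exclusion. However, exclusion depends on a major violation judged at data review, and missing diaries are not named.

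**FA entry and time zero may not survive a lost diary.** Drug intake times are recorded in the diary (Protocol 8.3). A dose can still be shown from the ORS record in the CRF (Protocol 4.1) or from returned drug (SAP 5.5.1), but the start time may be lost. This is a further gap and does not answer the point.

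**The large figures need extreme inputs.** This stands. The children must lose the diary yet attend and be rated, and all losses must fall in one arm. A reader might infer unequal loss because only one arm records racecadotril intake. Protocol 8.3 weakens that inference: the diary also asks for every stool, its consistency, ORS, other liquids and daily temperature, with no distinction between arms.

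**A reader might also infer that a rating of complete relief should count as the event, dated at Visit 2.** The documents do not support this.
- Protocol 4.2 justifies the open-label design by an objectively measured endpoint, and the GPA is an unblinded judgement.
- Such dating is imputation, which SAP 4.2 rules out.
- A GPA of 2, also a success, would stay at 144 h.
- The GPA appears in no flow chart, so a Visit 2 time is itself inferred.
- The visit is planned for Day 6 or as follows: "The same day, or within 24 hours after recovery, the parent(s)/caregiver(s) will visit the site for the end of treatment visit of the child". If these families come on Day 6, false positives with six control diaries lost are still about 8-9%.

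**Conclusion.** The point holds as a conflict between rules whose literal outcome is wrong for one kind of child. It is worth correcting before database lock, but it does not show that the trial's error rate is out of control. With roughly equal losses the cost is a few points of power, still far above the planned 80%, and false positives do not rise. With losses in one arm only, the bias is material: about 8% and 20% one-sided false positives with three and six control diaries lost, and about 82% and 50% power with three and six racecadotril diaries lost.

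These sizes assume the loss counts, linear interpolation, the recovery table as a stand-in for time to last watery stool, and results from hospitalized children aged 3-60 months carried over to this trial. The conflict between the sections depends on none of these.

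**What to change.** In SAP 4.2.1, and through it 4.2.2 and the Cox model in 4.2.3:

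1. Apply the 144 h value only to subjects whose diary shows diarrhea not ended by the end of treatment.
2. State that FA subjects with no usable post-baseline diary stool record remain in the FA sample but contribute no time to the log-rank and Kaplan-Meier analysis, in line with SAP 4.2. Define usable before database lock.
3. Tabulate the number of these subjects and their GPA scores by arm.
4. Run the literal rule (these subjects at 144 h) as a sensitivity analysis.
5. Do not use the GPA to create a primary event.

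Narrowing the 144 h rule leaves a child whose diary stops before recovery or end of treatment without a rule. The same paragraph must state one; that case is separate from this point.

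The cost is one SAP paragraph, one small table and one rerun of existing code, with no new data. The downside is that a few FA subjects add nothing to the primary test, which assumes that diary loss is unrelated to outcome. In the simulation only recovered children were lost, which breaks that assumption and leaves 3.2-4.5% one-sided error where 2.5% is nominal. The counts by arm and the sensitivity analysis show whether this matters.
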